PROTOCOL TITLE: *Tolerability, Safety, and Efficacy of Tedizolid as Oral Treatment for Bone and Joint Infection*

Revised: 8/10/18 Version 1.6

INSTRUCTIONS:

- Prepare a document with the following sections. Note that, depending on the nature of what you are doing, certain sections below may not be applicable. Indicate this as appropriate.
- For any items described in the sponsor's protocol or other documents submitted with the application, you may reference the title and page numbers of these documents (include the Protocol Version date/number and Section number and/or heading). If you reference page numbers, attach those pages to this protocol. Limit attached pages to those referenced in this protocol.
- When you write a protocol, keep an electronic copy in iRIS. You will need to modify this copy when making changes.
- Omit starred (*) items if this is the activation of a protocol at a new site or sites that will be overseen by a principal investigator who will take separate and full responsibility for that site or those sites. Complete by describing information specific to the site(s). Do not repeat information in the approved protocol that applies to all site(s).

1) Protocol Title

Include the full protocol title as listed on the application form.

Tolerability, Safety, and Efficacy of Tedizolid as Oral Treatment for Bone and Joint Infections

2) HSC Review History

If you have submitted this protocol for review by an external HSC, provide the previous study identification number and provide details of the review including the HSC name, date of review, and HSC contact information.

No previous review.

3) Investigator

Include the principal investigator's name as listed on the Application for Human Research.

[name] MPH

4) Objectives*

Describe the purpose, specific aims, or objectives.

State the hypotheses to be tested.

PROTOCOL TITLE: *Tolerability, Safety, and Efficacy of Tedizolid as Oral Treatment for Bone and Joint Infection*

Revised: 8/10/18 Version 1.6

The objective of our study is to quantify the tolerability and safety of tedizolid for bone and joint infections, both hardware and non-hardware associated. The study will focus on tolerability (e.g., gastrointestinal), hematologic toxicities, and neurologic toxicities.

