No materials will be used to directly recruit patients. Flyers will be given to select Inpatient and Outpatient Clinic staff. Flyers will also be given to physicians outside Harbor UCLA Medical Center. Once the physician identifies a potential patient and receives verbal consent from the patient, the physician will call the study staff. At that point the study staff will screen the patient via phone and a waiver of written consent will be utilized for screening purposes only.

Describe the amount and timing of any payments to subjects.

The subjects will be paid in cash for their follow up visits. They will be paid \$30 for the visit on week 1, \$35 for the visit on week 2, \$40 for the visit on week 3, \$40 for the visit on week 4, \$45 for the visit on week 5, \$45 for the visit on week 6, and \$50 each visit for visits on weeks 7, 8, 9, 10, 11, 12 and 13.

The total amount of compensation will range between \$240 and \$585 based on the number of follow up visits the subject completes. All subjects will complete visits on Weeks 1,2,3,4,5, and 12. Subjects still taking the study drug at week 6 will be required to return for a Week 6 follow up visit. Subjects still taking the study drug at week 7 will be required to return for a week 7 follow up visit, and so on- while patients are receiving the study drug they will return for weekly follow up visits until they have completed the course, or until they have reached 12 weeks. Once subjects complete the course of the study drug, they will return for one additional weekly follow up visit (e.g. if a patient completes the study drug at 7 weeks, they will return for visits on weeks 1-8 and week 12). If subjects take the study drug for 12 weeks, they will return for a final follow up visit on week 13.

b) Inclusion and Exclusion Criteria*

Describe how you will screen for eligibility.

Describe the criteria that define who will be included or excluded in your final study sample.

For this investigation, we will use strict inclusion and exclusion criteria.

Inclusion criteria will include:

a) Treatment of bone and joint infection in which therapy for Gram-positive organisms is suspected or documented, as determined by the treating physician and treatment of at least 4 weeks is planned. Bone and joint infection and trauma-associated bone and joint infection will

PROTOCOL TITLE: *Tolerability, Safety, and Efficacy of Tedizolid as Oral Treatment for Bone and Joint Infection*

Revised: 8/10/18 Version 1.6

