- f) Severe hepatic dysfunction as defined by liver function tests (ALT, ALP, AST, total bilirubin) \geq 3.0 times the upper limit of normal. as determined by the following limits from a baseline CMP obtained within the past 7 days. If a CMP has not been performed within the past 7 days, baseline levels may be used from a CMP performed within the past 2 months as long as another CMP is performed on the day of enrollment and the subject's levels are within the following limits.
- g) Hypersensitivity to tedizolid or other oxazolidinone-class antibiotics or similar compounds.
- h) Ongoing antibiotic-associated colitis.
- i) A diet high in tyramine-containing foods such as pickled or fermented meats and cheeses, wine, or avocados per investigator discretion.
- j) Concurrent use of sodium picosulfate (brand names: Sodipic Picofast, Laxoberal, Laxoberon, Purg-Odan, Picolax, Guttalax, Namilax, Pico-Salax and Prepopik).
- k) Concurrent use of any monoamine oxidase inhibitors (MAOIs) or use of MAOIs within two weeks of starting the study medication.
- l) Previous participation in the study.
- m) Use of tedizolid for any condition in the past 3 months.

PROTOCOL TITLE: *Tolerability, Safety, and Efficacy of Tedizolid as Oral Treatment for Bone and Joint Infection*

Revised: 8/10/18 Version 1.6

n) Any other medical, psychological, or social condition that, in the opinion of the Investigator, would prevent the patient from fully participating in the study or would represent a concern for study compliance or constitute a safety concern to the patient.

c) Local Number of Subjects

Indicate the total number of subjects to be accrued locally.

We will enroll subjects until we obtain 50 subjects who are analyzable and have completed all follow-ups through 12 weeks. The attrition rate for this study is unclear but we estimate a possible attrition rate of 10%, which would require enrollment of approximately 55 subjects.

If applicable, distinguish between the number of subjects who are expected to be enrolled and screen, and the number of subjects needed to complete the research procedures (i.e., numbers of subjects excluding screen failures.)

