At each follow up visit, CBC and CMP (comprehensive chemistry panel including liver function tests) will be collected via a blood draw. This blood sample will be sent to Quest Diagnostics by the

PROTOCOL TITLE: *Tolerability, Safety, and Efficacy of Tedizolid as Oral Treatment for Bone and Joint Infection*

Revised: 8/10/18 Version 1.6

CTSI/CTRU, an outside laboratory that is contracted with the CTSI/CTRU to process blood samples. Additionally, standardized surveys (See Data Collection Fields V 1.0, Neuropathy Scale V 1.0, attached) will be administered about drug side effects and tolerability, and adverse events will be measured using the Medical Dictionary for Regulatory Activities Terminology (MedDRA) version 18.1 (or the most current version). At these follow up visits, we will also record data points relevant to defining the efficacy of the treatment, such as the duration of the antibiotic treatment, any unplanned surgical procedures prompted by inadequate infection control, recurrence of signs or symptoms of bone and joint infection, and any other relevant comments or observations from the subject. The subject will also be asked to bring their study drug medication bottle and medication diary in order to assess compliance. If a subject suspects pregnancy during a follow up visit, they will be given a pregnancy test and the study team will track their reported menstrual cycle. If the subject does become pregnant, they will be discontinued from the study drug. Study staff will follow and collect data on the course of the pregnancy and the health of the child for at least 6-8 weeks after delivery.

Patients with evidence of myelosuppression will continue to have weekly CBCs performed until resolution of the myelosuppression.

Subjects who are concurrently taking serotonergic agents while receiving the study drug will be monitored for signs and symptoms of serotonin syndrome at each scheduled follow-up visit. Symptoms of serotonin syndrome include agitation or restlessness, confusion, rapid heartbeat and high blood pressure, dilated (big) pupils, loss of muscle coordination or twitching muscles, muscle rigidity (stiffness), heavy sweating, diarrhea, headache, shivering and goose bumps.

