The study is descriptive and thus no formal statistical analysis plan has been performed. The number of subjects chosen (n=50) is based on a sample size believed to have sufficient power to reassure clinicians that tedizolid is safe, tolerable, and efficacious for the treatment of native bone and hardware-associated bone and joint infection.

Of note, confidence intervals for safety and efficacy will be calculated. Confidence intervals for outcomes of low incidence (e.g., thrombocytopenia) will be approximately +/-3 - 7%. E.g., assuming n=50 subjects, a low incidence outcome with a probability of 2.5% will have 95% confidence intervals of <0.1%-6.8%. Outcomes with probabilities farther from 0% or 100% will have wider confidence intervals. For example, we anticipate cure rate will be 80%, in which assuming n=50, 95% confidence intervals will be 69%-91%.

Provide a power analysis.

Confidence intervals for safety and efficacy will be calculated. Confidence intervals for outcomes of low incidence (e.g., thrombocytopenia) will be approximately +/-3 - 7%. E.g., assuming n=50 subjects, a low incidence outcome with a probability of 2.5% will have 95% confidence intervals of <0.1%-6.8%. Outcomes with probabilities farther from 0% or 100% will have wider confidence intervals. For example, we anticipate cure rate will be 80%, in which assuming n=50, 95% confidence intervals will be 69%-91%.

Describe the steps that will be taken to secure the data (e.g., training, authorization of access, password protection, encryption, physical controls, certificates of confidentiality, and separation of identifiers and data) during storage, use, and transmission.

All source documents and specimens will be coded meaning these items will be labeled the subjects Study ID number and will include dates (case report forms) rather than his/her name and/or date of birth. We will maintain a separate password-protected key list/log (electronic file) linking each subject to their Study ID and a hardcopy will be maintained separate from individual subject files in a separate locked filing cabinet. Access to study computers and files will be limited to study personnel. Human research records including Informed Consent Forms

PROTOCOL TITLE: *Tolerability, Safety, and Efficacy of Tedizolid as Oral Treatment for Bone and Joint Infection*

Revised: 8/10/18 Version 1.6

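### Safety is to be summarised only by confidence intervals illustrated with event proportions; add a prespecified analysis of change in the counts and neuropathy score already recorded, because 50 subjects give little sensitivity to a modest mean fall

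*Combined protocol and SAP*

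**What the plan says.** Section 4 (Objectives) sets the priority: "The study will focus on tolerability (e.g., gastrointestinal), hematologic toxicities, and neurologic toxicities".

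Section 9(g) (Procedures) describes the data: "At each follow up visit, CBC and CMP (comprehensive chemistry panel including liver function tests) will be collected via a blood draw". Section 9(a) gives the minimum schedule: "All subjects will complete visits on Weeks 1,2,3,4,5, and 12". Weekly visits continue while the subject is on drug, and one further weekly visit follows the end of the course. Each completer therefore has 6 to 13 post-baseline results, at least one of them off drug. Section 9(g) also says that laboratory values are collected with their limits of normal and dates, and lists the neuropathy survey among those given at enrolment and follow-up.

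On analysis, Section 9(i) says "The study is descriptive and thus no formal statistical analysis plan has been performed". It then promises confidence intervals for safety and efficacy: "Confidence intervals for outcomes of low incidence (e.g., thrombocytopenia) will be approximately +/-3 - 7" per cent. Two worked examples follow, both proportions: "assuming n=50 subjects, a low incidence outcome with a probability of 2.5% will have 95% confidence intervals of <0.1%-6.8" per cent, and "we anticipate cure rate will be 80%, in which assuming n=50, 95% confidence intervals will be 69%-91" per cent. The power analysis repeats the same text. No section plans a change from baseline, a nadir or a time course for any laboratory value or for the neuropathy score. No section defines on-treatment thrombocytopenia or anaemia: the limits in Section 9(b) are for eligibility, and the cut-offs in Table 1 of Section 10 come from earlier 6-day trials.

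**The concern.** The haematologic worry that the protocol itself raises is a gradual one. Section 10 reports a possible dose and duration effect on haematologic parameters in 21-day Phase 1 studies, and this trial gives the drug for 4 to 12 weeks. A gradual effect would first appear as a shift in the whole distribution of counts, and only later as subjects crossing a cut-off. A proportion from 50 subjects responds weakly to such a shift; a within-subject mean change responds much more strongly.

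Section 9(i) also says that 50 subjects are believed enough to reassure clinicians about safety. If the report shows only that zero or one subject had thrombocytopenia, that result is nearly as likely with a modest fall as without one. Choosing a numeric analysis after seeing the data would carry less weight than having named it beforehand.

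**Working it through.** **1. The plan's own figures.** Wald interval, p ± 1.96 × √(p(1−p)/50):
- p = 2.5%: half-width 4.3%, interval −1.8% to 6.8%. This matches the stated upper limit, with the lower limit truncated.
- p = 80%: 68.9% to 91.1%. Matches.
- Half-width 2.8% at p = 1% and 7.1% at p = 7%. Matches the stated 3 to 7.

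The Wald form is poor at such low counts. Exact 95% limits are 0 to 7.1% for 0/50 and 0.05 to 10.6% for 1/50, so the data could hardly separate no events from one.

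**2. Inputs for the comparison.** From the protocol: n = 50; entrants above 150 (Section 9(b)); the cut-off of 112 for the lowest post-baseline platelet value, with a rate of 2.3% (Section 10, Table 1). Assumed: baseline normal with mean 300 and SD 80, truncated at 150; SD of within-subject change 50; mean fall 20. Units are x10^3/mm3.

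**3. Counting, one post-baseline draw per subject (simulation).**
- No fall: 1.0% below 112, so 0.5 expected events in 50.
- Fall of 20: 2.0%, so 1.0 expected event.
- Chance of seeing 0 or 1 event: 91% with no fall, 73% with the fall.

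**4. Counting, lowest of four on-drug draws.** This is nearer to Table 1's definition, and a 4-week course has four on-drug visits. Between-visit correlation of changes is assumed to be 0.5 to 0.7.
- No fall: 2.3-2.7%, about 1.1-1.4 events.
- Fall of 20: about 4.2-5.0%, about 2.1-2.5 events.
- If four or more events were taken as a signal, the binomial tail at 4.2-5.0% gives a 16-24% chance of reaching it, against 3-5% with no fall.

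**5. Paired mean change, same fall, two-sided 5%.**
- 95% half-width = t(0.975, 49) × 50/√50 = 2.01 × 7.07 = 14.
- Noncentrality = 20/7.07 = 2.83; power 79%.
- For change SD 40 to 80: half-width 11 to 23, power 93% down to 41%, fall detectable with 80% power 16 to 32.

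**6. Cross-check in SD units.** Counting is tested against the 2.3% rate, with a normal shift and a rejection rule of at least 4 or at least 5 events (exact one-sided alpha 0.028 or 0.006). The paired test assumes a baseline to on-treatment correlation of 0.5 to 0.7.
- Fall of 0.25 SD: counting 5-14%, paired 41-61%.
- Fall of 0.4 SD: counting 14-30%, paired 79-95%.
- Fall of 0.5 SD: counting 25-44%, paired 93-99%.
- Fall of 1 SD: counting 92-97%, paired above 99%.
- Fall detectable with 80% power: 0.76-0.87 SD by counting, 0.31-0.40 SD by mean change.
- A doubling of the 2.3% rate is detected with 8-20% power.
- Haemoglobin, against the 3.1% rate in Table 1 (at least 5 events): counting has 12%, 28% and 43% power for falls of 0.25, 0.4 and 0.5 SD, and 98% for 1 SD.

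The inputs in step 2 favour the paired analysis somewhat: a change SD of 50 against a baseline SD of 80 implies a correlation of about 1 − (50/80)²/2 = 0.80.

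**The case against.** The strongest reply is that the plan does not say what a critic may read into it. Thrombocytopenia is only an example, no threshold is set, and nothing forbids a numeric analysis. A reader might infer that every subject's results will be reduced to one yes/no event. The documents do not say so; they only name no other analysis.

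A reader might also infer that any real fall would very probably be missed. That does not follow. Falls of about 1 SD would be found by counting. Section 9(k) provides monthly investigator review and quarterly Data Safety Monitor review of laboratory results and neuropathy scales, and Section 9(g) continues weekly counts until myelosuppression resolves, so marked falls in single subjects would be seen. What these reviews lack is a numerical rule or an estimate of a group-wide decline. Section 9(k) refers to statistically significant side effects but names no test or comparator.

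Four limits on the remedy also stand:
- The baseline count may be a chart value up to 14 days old (Section 9(b)), possibly from acute illness, whereas follow-up samples go to an outside laboratory.
- An on-drug versus off-drug contrast would not suit neuropathy, which Section 5 says may be irreversible with linezolid: lasting harm would show no difference and look reassuring.
- Subjects withdrawn for cytopenia or neuropathy need make no further visits (Section 9(l)), so off-drug values may be missing for a reason related to toxicity.
- Proportions should not be demoted. The external haematology benchmarks in Section 10 are proportions, and a mean can hide severe toxicity in a few subjects.

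That the study is descriptive is no answer, since a mean change with a confidence interval is itself descriptive.

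**Conclusion.** The point holds as a cheap improvement to the analysis plan, not as a flaw that invalidates the trial. For modest falls, of about 0.25 to 0.5 SD, event counting in 50 subjects has roughly 5-44% power for platelets, where the paired mean change has 41-99%. In the worked case, the event count moves by about half an event on one draw, or about one event on the lowest of four, while the mean change is estimated to within ±14.

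The size depends on assumed means, SDs and correlations, on normality, and on an implied comparison with 6-day rates, because the plan specifies no test. With a change SD of 80, even the paired analysis has only 41% power for a fall of 20. The documents do not establish that a fall of 20 matters clinically. The direction of the comparison is the same throughout the range examined.

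**What to change.** In Section 9(i), keep the incidence proportions and add beside them:
- a prespecified repeated-measures estimate of mean change from the pre-treatment value, by week, with 95% confidence intervals, for platelets, haemoglobin, white cells, ALT and neuropathy score;
- the on-drug nadir for the same measures (for the neuropathy score, the worst on-drug value), also with 95% confidence intervals;
- the date of each baseline sample, so that the age of the baseline can be reported;
- for blood counts only, and as exploratory, the difference between the last on-drug and the first off-drug value, with a note on values missing after withdrawal.

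The proportions also need a stated on-treatment definition, which the protocol does not give.

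The cost is a little more analysis work; no visits, samples or subjects are added. The report should state that, with no control arm, a mean change cannot by itself be attributed to the drug, since resolving infection, surgery or regression to the mean could produce part of it.

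### The power section's 95% interval for a 2.5% toxicity at n=50 is a normal-approximation interval whose upper limit is too low; exact upper limits for 1 and 2 events are 10.6% and 13.7%, and no interval method is named

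*Combined protocol and SAP*

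**What the plan says.** Section 9(i) of the protocol, Data Management, states that the study is descriptive and has no formal statistical analysis plan. It describes n=50 as "a sample size believed to have sufficient power to reassure clinicians that tedizolid is safe, tolerable, and efficacious" and adds that "confidence intervals for safety and efficacy will be calculated", without saying how.

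Three precision figures follow. They appear first under the data analysis plan and again as the answer to the request for a power analysis:

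- A general statement: "Confidence intervals for outcomes of low incidence (e.g., thrombocytopenia) will be approximately +/-3 - 7"%.
- A rare-outcome example: "a low incidence outcome with a probability of 2.5% will have 95% confidence intervals of <0.1%-6.8"%.
- An efficacy example: "we anticipate cure rate will be 80%, in which assuming n=50, 95% confidence intervals will be 69%-91"%.

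The number 50 is the target for completers in section 9(c): "We will enroll subjects until we obtain 50 subjects who are analyzable and have completed all follow-ups through 12 weeks".

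**The concern.** An outcome with a 2.5% probability produces 1.25 expected events in 50 patients. With so few events the sampling distribution is strongly skewed, and a symmetric normal-approximation interval understates the upper limit. For a toxicity, the upper limit is the one that matters.

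Tolerability and haematologic and neurologic toxicity are the stated focus of the trial (section 4), and thrombocytopenia is the plan's own example of a rare outcome. The 2.5% rate is also close to the 2.3% low-platelet rate that Table 1 in section 10 reports after six days of treatment. A reader of section 9(i) would conclude that 50 patients can bound such a toxicity below 7%. If they cannot, the only quantitative support for the chosen sample size is too favourable. And since no method is named, the final report could reasonably follow the one its own examples imply.

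**Working it through.** **Inputs, all from section 9(i):** n = 50; p = 2.5%, with stated interval <0.1% to 6.8%; p = 80%, with stated interval 69% to 91%; confidence level 95%. Sidedness is not stated. Two limits are given, so two-sided is assumed.

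**1. Reproduce the plan's figures.** The Wald interval is p ± 1.96 × √(p(1−p)/n).

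- p = 0.025: √(0.025 × 0.975/50) = 0.02208, half-width 4.33 points, limits **−1.83% to 6.83%**. The upper limit matches the stated 6.8%.
- p = 0.80: √(0.8 × 0.2/50) = 0.05657, half-width 11.09 points, limits **68.9% to 91.1%**. This matches the stated 69-91%. Clopper-Pearson at 40/50 gives 66.3-90.0% and Wilson 67.0-88.8%, neither of which matches.

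Both examples therefore point to Wald. That the printed lower limit of <0.1% replaces the negative value is an inference. The methods tried that have a clearly positive lower limit at 2.5% (Clopper-Pearson, Wilson, Jeffreys) have upper limits of 9.8% or more.

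**2. Other methods at the same 2.5% (1.25/50), upper limits:** Jeffreys 9.8%, Wilson 11.3%, Clopper-Pearson 11.4%, Agresti-Coull 12.2%. A one-sided 95% exact limit would be 9.9%. None is near 6.8%.

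**3. Observable results.** A count of 1.25 cannot occur. The Clopper-Pearson limits for x events are the 2.5% quantile of Beta(x, n−x+1) and the 97.5% quantile of Beta(x+1, n−x); the lower limit is 0 when x = 0.

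| Events/50 | Estimate | Exact 95% interval | Half of total width (points) | Upper arm (points) | Wilson upper | Jeffreys upper |
|---|---|---|---|---|---|---|
| 0 | 0% | 0-7.1% | 3.6 | 7.1 | 7.1% | 4.9% |
| 1 | 2% | 0.05-10.6% | 5.3 | 8.6 | 10.5% | 9.0% |
| 2 | 4% | 0.5-13.7% | 6.6 | 9.7 | 13.5% | 12.2% |
| 3 | 6% | 1.3-16.5% | 7.6 | 10.5 | 16.2% | 15.2% |

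The general ±3 to 7 points is roughly right as half the total exact width. A symmetric ± nevertheless hides the upper arm, which is 7 to 10.5 points for 0 to 3 events.

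**4. Size of the understatement.** Against the stated 6.8%: 10.65/6.8 = 1.57 at one event, and 13.71/6.8 = 2.02 at two.

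**5. What a true 2.5% rate would produce.** Under Binomial(50, 0.025), P(0) = 0.282, P(1) = 0.362 and P(2) = 0.227. So P(at least one event) = 1 − 0.282 = 0.718, and in each such case the exact upper limit is at least 10.6%. Averaged over all outcomes it is 11.2%.

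**6. For scale.** At an observed 2.5%, exact intervals are 0.5-7.1% for 3/120 and 0.7-6.3% for 4/160. An upper limit near 6.8% thus corresponds to roughly 120-160 patients.

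**7. If Wald were used in the report.** Summing binomial probabilities over the counts whose Wald interval contains the true rate gives coverage of about 72% at 2.5% and 39% at 1%. Zero events would give an interval of 0-0%.

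**The case against.** The strongest reply is that nothing has been miscalculated: 6.83% is the correct Wald limit, and replacing an impossible negative lower limit by a value near zero is ordinary truncation. That is right. The fault lies in the choice of method and in the precision claimed from it.

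A second point concerns size. The factor of 2.0 compares an exact limit at an observed 4% with a Wald limit computed at 2.5%. With both methods at the same estimate, the ratio is 11.4/6.8 = 1.7 at 2.5%, 10.6/5.9 = 1.8 at 1/50 and 13.7/9.4 = 1.45 at 2/50. Clopper-Pearson is also conservative, covering 99.2% at a true 2.5%, and Jeffreys at 2.5% gives 9.8/6.8 = 1.4. The exact size therefore depends on the comparator, but every usual alternative exceeds 6.8% at 1/50 and 2/50. The 1.6 to 2.0 range remains a fair description because the plan's 2.5% is a true probability, whose likely results are 0, 1 or 2 events.

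Third, the study is a pilot that calls itself exploratory and descriptive. No test, threshold or stopping rule uses the 6.8%, the plan does not commit to Wald for the report, and correct intervals can be computed later from the same data. All of this stands and limits the consequences. It does not remove the problem: in a descriptive study the intervals are the inference, and these figures are the only numerical justification of n=50.

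**Conclusion.** The concern holds. The rare-outcome example is a Wald interval applied at about one expected event, and its upper limit of 6.8% is too low by a factor of about 1.6 (1/50) to 2.0 (2/50) against two-sided 95% Clopper-Pearson limits. Even zero events give an exact or Wilson upper limit of 7.1%; only a less conservative choice at zero events (Jeffreys 4.9%, one-sided exact 5.8%) falls below the stated figure.

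The conclusion assumes a two-sided 95% interval, 50 analysable patients and a simple binomial proportion. The 80% cure example is only modestly affected. The point should be fixed because it concerns the toxicity outcomes the trial exists to quantify, but it changes how the precision is read and not how the trial is run.

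**What to change.** In both paragraphs of section 9(i):

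- Name one interval method for all proportions, Clopper-Pearson or Wilson, and state that intervals are two-sided 95%.
- Replace the 2.5% example with observable results. By Clopper-Pearson: 0/50, 0-7.1%; 1/50, 0.05-10.6%; 2/50, 0.5-13.7%.
- Replace the symmetric ±3 to 7 statement with these asymmetric limits.
- Replace the claim of sufficient power with what 50 patients deliver: zero events would exclude a true rate above about 7% (two-sided 95%).
- Restate the cure example by the same method (exact: 66-90% at 40/50).

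The cost is wording in two paragraphs and a less favourable statement of precision. No extra patients are needed, and neither conduct nor data collection changes.
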